#### ***7.1.2.7.1 Active follow-up with clinic visits***

Added text:

- Recording of cytotoxic chemotherapy and radiotherapy for any new primary malignancy

#### ***7.1.2.7.2 Active follow-up without scheduled clinic visits***

Added text:

- Recording of cytotoxic chemotherapy and radiotherapy for any new primary malignancy

#### ***7.1.2.8.1 End of active follow-up with clinic visits***

Added text:

- Recording of cytotoxic chemotherapy and radiotherapy for any new primary malignancy

Old text:

All study subjects will be eligible for further follow-up either in this study or in a separate long-term follow-up study for up to 7 years. The separate long-term follow-up study has been set up to follow subjects who received radium-223 dichloride or placebo in the course of Bayer-sponsored clinical trials. The long-term follow-up study has a specific focus on investigator reported, radium-223 dichloride-related AEs and serious AEs, ~~hematologic toxicity (e.g., myelosuppression / myelofibrosis / bone marrow aplasia), new primary malignancies, including leukemias and solid tumors,~~ and survival for up to 7 years after last dose of radium-223 dichloride or until death. During long-term follow-up, subjects will be contacted every 6 months by telephone. All subjects who transition into this separate long-term follow-up study will require a separate signed informed consent.

New text:

All study subjects will be eligible for further follow-up either in this study or in a separate long-term follow-up study for up to 7 years. The separate long-term follow-up study has been set up to follow subjects who received radium-223 dichloride or placebo in the course of Bayer-sponsored clinical trials. The long-term follow-up study has a specific focus on investigator reported, radium-223 dichloride-related AEs and serious AEs, all occurrences of leukemia, myelodysplastic syndrome, aplastic anemia, primary bone cancer or any other new primary malignancy, cancer treatment (including any systemic cytotoxic chemotherapy or radiotherapy for any malignancy; all systemic anti-cancer therapies for prostate cancer, including androgen synthesis inhibitors / androgen-receptor antagonists, systemic radioisotopes and radiation treatment; excluding analgesics), in subjects who receive cytotoxic chemotherapy: all occurrences of febrile neutropenia or hemorrhage during their chemotherapy treatment and for up to 6 months thereafter, and survival for up to 7 years after last dose of radium-223 dichloride or until death. During long-term follow-up, subjects, their treating health care professional, or caregiver will be contacted every 6 months by telephone. All subjects who transition into this separate long-term follow-up study will require a separate signed informed consent. Subject data collected at other standard-of-care visits and / or contacts may be used to satisfy study-required data.

#### **7.1.2.8.2 End of active follow-up without scheduled clinic visits**

Added text:

- Recording of cytotoxic chemotherapy and radiotherapy for any new primary malignancy

Old text:

All study subjects will be eligible for further follow-up either in this study or in a separate long-term follow-up study for up to 7 years. The separate long-term follow-up study has been set up to follow subjects who received radium-223 dichloride or placebo in the course of Bayer-sponsored clinical trials. The long-term follow-up study has a specific focus on investigator reported, radium-223 dichloride-related AEs and serious AEs, ~~hematologic toxicity (e.g., myelosuppression / myelofibrosis / bone marrow aplasia), new primary malignancies, including leukemias and solid tumors~~, and survival for up to 7 years after last dose of radium-223 dichloride or until death. During long-term follow-up, subjects will be contacted every 6 months by telephone. All subjects who transition into this separate long-term follow-up study will require a separate signed informed consent.

New text:

All study subjects will be eligible for further follow-up either in this study or in a separate long-term follow-up study for up to 7 years. The separate long-term follow-up study has been set up to follow subjects who received radium-223 dichloride or placebo in the course of Bayer-sponsored clinical trials. The long-term follow-up study has a specific focus on investigator reported, radium-223 dichloride-related AEs and serious AEs, all occurrences of leukemia, myelodysplastic syndrome, aplastic anemia, primary bone cancer or any other new primary malignancy, cancer treatment (including any systemic cytotoxic chemotherapy or radiotherapy for any malignancy; all systemic anti-cancer therapies for prostate cancer, including androgen synthesis inhibitors / androgen-receptor antagonists, systemic radioisotopes and radiation treatment; excluding analgesics), in subjects who receive cytotoxic chemotherapy: all occurrences of febrile neutropenia or hemorrhage during their chemotherapy treatment and for up to 6 months thereafter, and survival for up to 7 years after last dose of radium-223 dichloride or until death. During long-term follow-up, subjects, their treating health care professional, or caregiver will be contacted every 6 months by telephone. All subjects who transition into this separate long-term follow-up study will require a separate signed informed consent. Subject data collected at other standard-of-care visits and / or contacts may be used to satisfy study-required data.

#### **7.1.2.9 Long-term follow-up to 7 years following last dose**

Old text:

This period starts when subjects have completed the active follow-up period and ends 7 years after the last dose of radium-223 dichloride or when the subject dies. All study subjects will be eligible for further follow-up either in this study or in a separate long-term follow-up study for up to 7 years. The separate long-term follow-up study has been set up to follow subjects who received radium-223 dichloride or placebo in the course of Bayer-sponsored clinical trials. The long-term follow-up study has a specific focus on investigator reported radium-223 dichloride-related AEs and SAEs, ~~hematologic toxicity (e.g., myelosuppression /~~

~~myelofibrosis / bone marrow aplasia), new primary malignancies, including leukemias and solid tumors, and survival for up to 7 years after last dose of radium-223 dichloride or until death. During long-term follow-up, subjects will be contacted every 6 months by telephone. All subjects who transition into this separate long-term follow-up study will require a separate signed informed consent.~~

New text:

This period starts when subjects have completed the active follow-up period and ends 7 years after the last dose of radium-223 dichloride or when the subject dies. All study subjects will be eligible for further follow-up either in this study or in a separate long-term follow-up study for up to 7 years. The separate long-term follow-up study has been set up to follow subjects who received radium-223 dichloride or placebo in the course of Bayer-sponsored clinical trials. The long-term follow-up study has a specific focus on investigator reported radium-223 dichloride-related AEs and SAEs, all occurrences of leukemia, myelodysplastic syndrome, aplastic anemia, primary bone cancer or any other new primary malignancy, cancer treatment (including any systemic cytotoxic chemotherapy or radiotherapy for any malignancy; all systemic ant-cancer therapies for prostate cancer, including androgen synthesis inhibitors / androgen-receptor antagonists, systemic radioisotopes and radiation treatment; excluding analgesics), in subjects who receive cytotoxic chemotherapy: all occurrences of febrile neutropenia or hemorrhage during their chemotherapy treatment and for up to 6 months thereafter, and survival for up to 7 years after last dose of radium-223 dichloride or until death. During long-term follow-up, subjects, their treating health care professional, or caregiver will be contacted every 6 months by telephone. All subjects who transition into this separate long-term follow-up study will require a separate signed informed consent. Subject data collected at other standard-of-care visits and / or contacts may be used to satisfy study-required data.

#### **7.1.2.9.1 Long-term follow-up (via telephone follow-up)**

Old text:

Subjects will be contacted by telephone every 6 months ( $\pm$  14 days) for 7 years following the last study treatment or until death to determine the following:

- Survival status
- All SAEs occurring during this period have to be documented and reported if considered to be related to study medication. Concomitant ~~medication~~ associated with these events will not be collected. If a subject is unable to provide required details for events of interest, this information ~~may~~ need to be obtained from the primary provider.
- Recording of new primary malignancies
- All occurrences of hematological conditions such as myelodysplastic syndrome, aplastic anemia, myelofibrosis, and primary bone cancer or any other new primary malignancy, such as acute myeloid leukemia, must be reported as SAEs at any time and regardless of the investigator's causality assessment.

Since this information will be collected over the telephone from the subject, it is the clinical site's responsibility to obtain and make available the source documentation for the information collected from the subject and document it in the eCRF.

New text:

Subjects, their treating health care professional, or caregiver will be contacted by telephone every 6 months ( $\pm$  14 days) for 7 years following the last study treatment or until death to determine the following:

- Survival status
- Recording of prostate cancer therapies
- All radium-223 dichloride/placebo related adverse events (AEs)
- All SAEs occurring during this period have to be documented and reported if considered to be related to study medication. Concomitant treatment associated with these events will not be collected unless it is cancer medication / treatment (including any systemic cytotoxic chemotherapy or radiotherapy for any malignancy; all systemic ant-cancer therapies for prostate cancer, including androgen synthesis inhibitors / androgen-receptor antagonists, systemic radioisotopes and radiation treatment; excluding analgesics). If a subject is unable to provide required details for events of interest, this information will need to be obtained from the primary provider.
- Recording of new primary malignancies
- Recording of cytotoxic chemotherapy and radiotherapy for any new primary malignancy
- All occurrences of hematological conditions such as myelodysplastic syndrome, aplastic anemia, myelofibrosis, and primary bone cancer or any other new primary malignancy, such as acute myeloid leukemia, must be reported as SAEs at any time and regardless of the investigator's causality assessment
- In subjects who receive cytotoxic chemotherapy: all occurrences of febrile neutropenia or hemorrhage during their chemotherapy treatment and for up to 6 months thereafter.

Subject data collected at other standard-of-care visits and / or contacts may be used to satisfy study-required data.

Since this information will be collected over the telephone from the subject, their treating health care professional, or caregiver, it is the clinical site's responsibility to obtain and make available the source documentation for the information collected from the subject and document it in the eCRF.

Training for conducting the follow-up contacts will be provided to clinical site personnel including, but not limited to, use of a telephone script. Subject data collected at other standard-of-care visits and / or contacts may be used to satisfy study-required data.

#### 7.1.2.9.2 *End of long-term follow-up*

Old text:

The end of study procedures for subjects who are in the long-term follow-up period will include the following:

- Survival status
- All SAEs have to be documented and reported if considered to be related to study medication. Concomitant ~~medication~~ associated with these events will not be collected. If a subject is unable to provide required details for events of interest, this information ~~may~~ need to be obtained from the primary provider.
- Recording of new primary malignancies
- All occurrences of hematological conditions such as myelodysplastic syndrome, aplastic anemia, myelofibrosis, and primary bone cancer or any other new primary malignancy, such as acute myeloid leukemia, must be reported as SAEs at any time and regardless of the investigator's causality assessment.

Since this information will be collected over the telephone from the subject, it is the clinical site's responsibility to obtain and make available the source documentation for the information collected from the subject and document it in the eCRF.

New text:

The end of study procedures for subjects who are in the long-term follow-up period will include the following:

- Survival status
- Recording of prostate cancer therapies
- All SAEs occurring during this period have to be documented and reported if considered to be related to study medication. Concomitant treatment associated with these events will not be collected unless it is cancer medication / treatment (including any systemic cytotoxic chemotherapy or radiotherapy for any malignancy; all systemic ant-cancer therapies for prostate cancer, including androgen synthesis inhibitors / androgen-receptor antagonists, systemic radioisotopes and radiation treatment; excluding analgesics). If a subject is unable to provide required details for events of interest, this information will need to be obtained from the primary provider.
- Recording of new primary malignancies
- Recording of cytotoxic chemotherapy and radiotherapy for any new primary malignancy
- All occurrences of hematological conditions such as myelodysplastic syndrome, aplastic anemia, myelofibrosis, and primary bone cancer or any other new primary

malignancy, such as acute myeloid leukemia, must be reported as SAEs at any time and regardless of the investigator's causality assessment

- In subjects who receive cytotoxic chemotherapy: all occurrences of febrile neutropenia or hemorrhage during their chemotherapy treatment and for up to 6 months thereafter.

Subject data collected at other standard-of-care visits and / or contacts may be used to satisfy study-required data.

Since this information will be collected over the telephone from the subject, their treating health care professional, or caregiver, it is the clinical site's responsibility to obtain and make available the source documentation for the information collected from the subject and document it in the eCRF.

#### **Change 5**

##### ***Synopsis-Plan for statistical analysis***

Old text:

Both comparisons will be performed at the time of final analysis, after the latest of (1) approximately 135 SSE-FS events in subjects included in Comparison 1 as defined below; (2) approximately 75 SSE-FS events following ~~Week 24~~ in subjects included in Comparison 2 as defined below, and (3) the last subject has been followed for 30 days from last treatment. In

the event the applicable number of events is not reached, the primary endpoint analysis will mature 7 years after the last subject has received last treatment.

Comparison 2: No further radium-223 dichloride treatment versus extended dosing: SSE-FS analysis from ~~24 weeks~~ in subjects receiving standard-dose regimen

H02: In a population of subjects treated with a regimen of up to 6 doses of 50 kBq/kg (55 kBq/kg after implementation of NIST update) (standard dose) radium-223 dichloride who survived SSE-free and are eligible for further radium-223 dichloride treatment at 24 weeks, population SSE-FS beyond ~~24 weeks~~ in subjects treated with a regimen of up to an additional 6 doses of 50 kBq/kg (55 kBq/kg after implementation of NIST update) (extended dose) radium-223 dichloride is equal to population SSE-FS beyond ~~24 weeks~~ in subjects receiving no further radium-223 dichloride treatment beyond the standard dose regimen, versus

HA2: In a population of subjects treated with a regimen of up to 6 doses of 50 kBq/kg (55 kBq/kg after implementation of NIST update) (standard dose) radium-223 dichloride who survived SSE-free and are eligible for further radium-223 dichloride treatment at 24 weeks, population SSE-FS beyond ~~24 weeks~~ in subjects treated with a regimen of up to an additional 6 doses of 50 kBq/kg (55 kBq/kg after implementation of NIST update) (extended dose) radium-223 dichloride is greater than population SSE-FS beyond ~~24 weeks~~ in subjects receiving no further radium-223 dichloride treatment beyond the standard dose regimen.

Comparison 2 will be an analysis of SSE-FS from ~~24 weeks from randomization~~ in subjects surviving SSE-free to ~~24 weeks completing and / or not discontinued from treatment~~. It will compare subjects in Treatment Arm A with subjects in Treatment Arm C.

New text:

Both comparisons will be performed at the time of final analysis, after the latest of (1) approximately 135 SSE-FS events in subjects included in Comparison 1 as defined below; (2) approximately 75 SSE-FS events following the 6th dose in subjects included in Comparison 2 as defined below, and (3) the last subject has been followed for 30 days from last treatment. In the event the applicable number of events is not reached, the primary endpoint analysis will mature 7 years after the last subject has received last treatment.

Comparison 2: No further radium-223 dichloride treatment versus extended dosing: SSE-FS analysis from the date of the 6th dose in subjects receiving standard-dose regimen

H02: In a population of subjects treated with a regimen of up to 6 doses of 50 kBq/kg (55 kBq/kg after implementation of NIST update) (standard dose) radium-223 dichloride who survived SSE-free and are eligible for further radium-223 dichloride treatment at 24 weeks, population SSE-FS beyond the 6th dose in subjects treated with a regimen of up to an additional 6 doses of 50 kBq/kg (55 kBq/kg after implementation of NIST update) (extended dose) radium-223 dichloride is equal to population SSE-FS beyond the 6th dose in subjects

receiving no further radium-223 dichloride treatment beyond the standard dose regimen, versus

HA2: In a population of subjects treated with a regimen of up to 6 doses of 50 kBq/kg (55 kBq/kg after implementation of NIST update) (standard dose) radium-223 dichloride who survived SSE-free and are eligible for further radium-223 dichloride treatment at 24 weeks, population SSE-FS beyond the 6th dose in subjects treated with a regimen of up to an additional 6 doses of 50 kBq/kg (55 kBq/kg after implementation of NIST update) (extended dose) radium-223 dichloride is greater than population SSE-FS beyond the 6th dose in subjects receiving no further radium-223 dichloride treatment beyond the standard dose regimen.

Comparison 2 will be an analysis of SSE-FS from the 6th dose in subjects surviving SSE-free to the completion of the 6th dose. It will compare subjects in Treatment Arm A with subjects in Treatment Arm C.

#### **4.4 End of Study**

Old text:

The primary endpoint cut-off will be reached at the later of 1) 135 SSE-FS events in subjects included in Comparison 1 as defined in Section 8.4 below, and 2) 75 SSE-FS events following ~~Week 24~~ in subjects included in Comparison 2 as defined in Section 8.4 below, and 3) the last subject has been followed for 30 days from last treatment. In the event the applicable number of events is not reached, the primary endpoint analysis will mature 7 years after the last subject has received last treatment.

New text:

The primary endpoint cut-off will be reached at the later of 1) 135 SSE-FS events in subjects included in Comparison 1 as defined in Section 8.4 below, and 2) 75 SSE-FS events following the 6th dose in subjects included in Comparison 2 as defined in Section 8.4 below, and 3) the last subject has been followed for 30 days from last treatment. In the event the applicable number of events is not reached, the primary endpoint analysis will mature 7 years after the last subject has received last treatment.

#### **7.3.2 Definition of efficacy variables**

Old text:

In this study, time-to-event endpoints are defined with respect to 2 distinct start dates, randomization date and 24 weeks. Response and progression endpoints are defined with respect to 2 corresponding baselines, the screening (or pre-treatment) baseline and 24 weeks. Details on definitions of starting points and baselines will be provided in the SAP or in the imaging charter or other central reviewer documentation.

New text:

In this study, time-to-event endpoints are defined with respect to 2 distinct start dates, randomization date and the date of the 6th dose. Response and progression endpoints are defined with respect to 2 corresponding baselines, the screening (or pre-treatment) baseline

and the 6th dose date. Details on definitions of starting points and baselines will be provided in the SAP or in the imaging charter or other central reviewer documentation.

#### **7.3.5.6 Additional pain and health related quality of life endpoints**

Old text:

Subject-reported outcome data not described above, palliative pain relief procedure data, additional BPI-SF data collected at clinic visits, and pain data collected ~~following the Week 24 assessment~~, will be evaluated as described in the SAP.

New text:

Subject-reported outcome data not described above, palliative pain relief procedure data, additional BPI-SF data collected at clinic visits, and pain data collected will be evaluated as described in the SAP.

### **8.2 Analysis sets**

Old text:

**Week 24 (W24):** All ITT subjects in Arm A (standard dose) and Arm C (extended dosing) ~~treated with radium-223 dichloride and eligible for further treatment at W 24~~. The W24 dataset will be used for the analysis of efficacy endpoints related to Comparison 2 and associated evaluations. Subjects will be included in W24 analyses according to the treatment to which they were randomized.

New text:

**Week 24 (W24):** All ITT subjects in Arm A (standard dose) and Arm C (extended dosing) treated with radium-223 dichloride and eligible for further treatment at W 24 (i.e., 7th injection). Week 24 applies to subjects who received the 6th injection without any dose delays. As dose delays are allowed per protocol, 6th injection can occur after Week 24 for subjects who had dose delays. Hence, this population is defined based on the number of injections not based on the timing. The W24 dataset will be used for the analysis of efficacy endpoints related to Comparison 2 and associated evaluations. Subjects will be included in W24 analyses according to the treatment to which they were randomized.

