- b Once a separate, extended safety follow-up protocol, for the inclusion of subjects who received radium-223 dichloride in the course of Bayer sponsored clinical studies, has been implemented, the study subjects surviving after the end of the 2 years of active follow-up will be transitioned to this separate, extended safety follow-up protocol and the current study will be terminated at the time the last study subject is transitioned.
- c The maximum period for rescreening screen failed subjects is 35 days (14 days screening + 7-day window + 14 days for rescreening) from signing the ICF to randomization. Rescreening of a subject requires prior approval of the Bayer-designated medical representative (see Section 5.1). Eligibility should be confirmed within 14 ± 7 days of randomization.
- d The subject should return to the clinic in advance of the scheduled dose visit such that results of the laboratory assessment are available within 72 hours prior to dosing (each dose period is 28 ± 7 days after the prior dose of radium-223 dichloride).
- e Subjects who can no longer travel to the clinical site or who receive further anticancer therapy will only be followed up by telephone (active follow-up without clinic visits). Symptomatic skeletal events will not be collected over the phone.
- f The study record or subject's clinical record must clearly show that informed consent was obtained prior to any other study procedures being performed. Eligibility should be confirmed during the screening period and reconfirmed prior to dosing at Dose 1, Day 1.
- g Reconfirmation of eligibility and registration in the IVRS / IWRS: hematology results obtained within 72 hours of Dose 1, Day 1 should be reviewed and it should be confirmed that the values are still within the treatment ranges (absolute neutrophil count ≥ 1.5 x 10^9/L, platelet count ≥ 100 x 10^9/L, and hemoglobin ≥ 9.0 g/dL).

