**Change 5:**

Updated analysis for Comparison 2 from 24 weeks to 6th dose date

Sections affected included:

- Synopsis-Study objectives
- Synopsis-Plan for statistical analysis
- 2.0 Study objectives
- 4.4 End of study
- 7.3.2 Definition of efficacy variables
- 7.3.5.6 Additional pain and health related quality of life endpoints
- 8.2 Analysis sets
- 8.4.1 Primary efficacy analysis
- 8.4.2.2 Analyses of standard dosing and extended dosing from the 6th dose date
- 8.6 Determination of sample size

*Rationale:* The 'Week 24 baseline value' is defined as the last non-missing value on or before the date of the 6th injection. Ideally, this visit would be the date of the 7th injection for Arm C subjects and expected 7th injection date for Arm A subjects. However, the end of treatment visit (30±7 days from last dose) for Arm A subjects could be missing due to consent withdrawal or happen out of visit window. Hence, there is no comparable visit for Arm A subjects that could be used as the expected 7th injection date. To account for this and

achieve comparability between the two arms, the 6th injection date is used as the reference date for Comparison 2 subjects.

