H02: In a population of subjects treated with a regimen of up to 6 doses of 50 kBq/kg (55 kBq/kg after implementation of NIST standard update) (standard dose) radium-223 dichloride who survived SSE-free and are eligible for further radium-223 dichloride treatment at 24 weeks, population SSE-FS beyond the 6th dose in subjects treated with a regimen of up to an additional 6 doses of 50 kBq/kg (55 kBq/kg after implementation of NIST update) (extended dose) radium-223 dichloride is equal to population SSE-FS beyond the 6th dose in subjects receiving no further radium-223 dichloride treatment beyond the standard dose regimen, versus

HA2: In a population of subjects treated with a regimen of up to 6 doses of 50 kBq/kg (55 kBq/kg after implementation of NIST update) (standard dose) radium-223 dichloride who survived SSE-free and are eligible for further radium-223 dichloride treatment at 24 weeks, population SSE-FS beyond the 6th dose in subjects treated with a regimen of up to an additional 6 doses of 50 kBq/kg (55 kBq/kg after implementation of NIST update) (extended dose) radium-223 dichloride is greater than population SSE-FS beyond the 6th dose in subjects receiving no further radium-223 dichloride treatment beyond the standard dose regimen.

Comparison 2 will be an analysis of SSE-FS from the 6th dose, in subjects surviving completion of to the 6th dose. It will compare subjects in Treatment Arm A with subjects in Treatment Arm C.

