#### **8.4.2.2 Analyses of standard dosing and extended dosing from the 6th dose date**

Old text:

For the following secondary endpoint analyses, subjects will be classified into 2 treatment groups: (1) the “standard dose” treatment group, consisting of applicable ITT subjects in Treatment Arm A, and (2) the “extended dosing” treatment group, consisting of applicable ITT subjects in Treatment Arm C. For these analyses, the start date will be 24 weeks, and the 24 week ~~assessment~~ baseline will be used.

For secondary endpoint time-to-event analyses for these treatment groups, subjects included will have survived to the 24 week start date without having experienced the applicable event, and will have completed and / or not been discontinued from treatment. Details defining these analyses will be provided in the SAP.

New text:

For the following secondary endpoint analyses, subjects will be classified into 2 treatment groups: (1) the “standard dose” treatment group, consisting of applicable ITT subjects in Treatment Arm A, and (2) the “extended dosing” treatment group, consisting of applicable ITT subjects in Treatment Arm C. For these analyses except for rPFS, the 6th dose date will be used as the reference date. For rPFS, randomization date will be used as the reference date.

For secondary endpoint time-to-event analyses for these treatment groups, subjects included will have survived to the 6th dose date without having experienced the applicable event, and will have completed and / or not been discontinued from treatment. Details defining these analyses will be provided in the SAP.

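### Comparison 2 now starts at the 6th dose, but its W24 set and hypotheses still select on eligibility at the 7th injection about 4 weeks later, and the stated 80.6% power fits a 24-week start

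*Protocol*

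**What the plan says.** The current wording is taken from the Amendment 3 new text. The body of Section 8.2 lies in the part of the protocol not shown, and the Amendment 4 summary lists no change to it.

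- **Time zero.** The synopsis reads "Comparison 2 will be an analysis of SSE-FS from the 6th dose in subjects surviving SSE-free to the completion of the 6th dose". Sections 7.3.2, 8.4.1 and 8.6 use the same start.
- **Analysis set.** Section 8.2 limits the W24 set, which serves Comparison 2, to Arm A and Arm C subjects "treated with radium-223 dichloride and eligible for further treatment at W 24 (i.e., 7th injection". The same definition then adds: "Hence, this population is defined based on the number of injections not based on the timing".
- **Hypotheses.** H02 and HA2 concern subjects "who survived SSE-free and are eligible for further radium-223 dichloride treatment at 24 weeks", while counting SSE-FS beyond the 6th dose.
- **Primary analysis text.** Section 8.4.1 includes subjects with the garbled phrase "in subjects surviving completion of to the 6th dose".
- **Secondary endpoints.** Section 8.4.2.2 requires that subjects "will have completed and / or not been discontinued from treatment".
- **Schedule.** Table 7-1 puts dose 6 at Week 20 and dose 7 at Week 24; "each dose period is 28 ± 7 days after the prior dose of radium-223 dichloride". Section 6.4.7 allows at most 8 weeks between injections.
- **Reason for the change.** Amendment 3, Change 5, says the Arm A end-of-treatment visit (30 ± 7 days after the last dose) can be absent or off schedule. It concludes: "Hence, there is no comparable visit for Arm A subjects that could be used as the expected" 7th-injection date.

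**The concern.** A subject's membership in an analysis set should be known by the time follow-up starts. Here follow-up starts at the 6th dose, but Section 8.2 and the hypotheses ask about status at a visit some 28 days later. Events in that gap count towards the endpoint and can also decide who is in the set. The synopsis and Section 8.6 ask only for event-free status at the 6th dose, so the protocol gives incompatible populations for one primary superiority test.

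The two arms differ in how the later condition can be observed. Arm C has a scheduled 7th injection with pre-dose laboratory checks. Arm A has no further injection, and the protocol itself says no Arm A visit can stand in for that date. In Section 8.4.2.2, an Arm A subject can qualify by completing 6 doses, while an Arm C subject can still be discontinued. If gap failures left the set in Arm C more often than in Arm A, the comparison would lean towards extended dosing, which is declared superior at a one-sided p below 0.1.

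Moving time zero also affects the sample size. Section 8.6 assumes no difference between arms for the first 24 weeks, so a start at dose 6 (Week 20) adds about 4 weeks in which no effect is expected.

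**Working it through.** **1. Reproduce the stated power.** Section 8.6 gives 74.9 events, hazard ratio 0.606, one-sided alpha 0.10 and power 80.6%.
- Schoenfeld: √74.9 × |ln 0.606| / 2 − 1.2816 = 8.654 × 0.5009 / 2 − 1.2816 = 0.886, so power is 81.2%.
- Freedman: 8.654 × (1 − 0.606)/(1 + 0.606) − 1.2816 = 0.842, so power is 80.0%.
- Log-rank simulation with time zero at 24 weeks (132.8/2 ≈ 66 per arm, 75 events): 80.8%.

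The stated figure therefore fits a 24-week start with the full effect from time zero.

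**2. Numbers at a 6th-dose start.** Section 8.6 leaves 55.35% of 240 at 24 weeks. At a constant rate, the share at Week 20 is 0.5535^(20/24) = 0.611, and 0.611 × 240 = 146.6, or about 73 per arm.

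**3. Events in the gap.** With a 9-month median the hazard is ln 2/9 = 0.0770 per month. Four weeks is 0.92 month, so P(event) = 1 − exp(−0.0770 × 0.92) = 6.8%, about 5 of 73. For gaps of 3, 5 and 8 weeks it is 5.2%, 8.5% and 13.2%.

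**4. Type I error with no true effect.** Simulated SSE-FS is exponential with a 9-month median, 73 per arm, analysed at 75 events. Assumptions not in the protocol are uniform accrual over 18 months, a loss-to-follow-up hazard of 0.030 per month (back-calculated from 55.35%), and the share of Arm C gap events dropped.

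| Rule applied | Mean hazard ratio | One-sided type I error |
|---|---|---|
| No condition | 1.00 | 0.106 |
| Same condition in both arms, 4 weeks | 1.00 | 0.099 |
| Arm C only, 4 weeks, 25% dropped | 0.97 | 0.125 |
| Arm C only, 4 weeks, 50% dropped | 0.94 | 0.161 |
| Arm C only, 4 weeks, all dropped | 0.88 | 0.233 |
| Arm C only, 3 weeks, all dropped | 0.91 | 0.205 |
| Arm C only, 5 weeks, all dropped | 0.86 | 0.276 |
| Arm C only, 8 weeks, all dropped | 0.78 | 0.409 |

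Hand check of the 4-week, all-dropped row: √75 × ln 0.88 / 2 = −0.554, and Φ(−1.2816 + 0.554) = Φ(−0.728) = 0.233. A second simulation of that case (8,000 trials, about 55% of subjects with events) gives hazard ratio 0.88 and error 0.242.

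**5. Power at a 6th-dose start with no later condition.** If benefit begins only at the 7th injection, simulation at 75 events gives 72.0%. Hand check: about 5 gap events per arm carry no effect, so about 65 of 75 events carry it. The average log hazard ratio is 65/75 × 0.5009 = 0.434; √75 × 0.434 / 2 − 1.2816 = 0.598; power is about 72.5%.

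**The case against.** A reader might infer that eligibility is checked only in Arm C, and hence that the primary comparison is biased towards extended dosing as written. The documents do not support that.

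- Section 8.2 and H02/HA2 state one condition for both arms. Read literally, an Arm A subject with an event in the gap fails it too, and step 4 shows no inflation when both arms are treated alike.
- Arm A does have assessments at about that time: the end-of-treatment visit with blood count and chemistry, and Week 24 tumor imaging.
- The Amendment 3 rationale concerns a comparable date and adopts the 6th injection in order to align the arms. It does not say eligibility is judged in one arm.
- The synopsis, Section 8.6 and the number-of-injections sentence in Section 8.2 support a 6th-dose rule under which the bias cannot arise. The SAP, not shown, may settle this.
- No visible text makes a skeletal event end dosing, so it is not established that Arm C subjects with one in the gap would leave the set while Arm A subjects stay.
- The missing SSE-free wording in Section 8.4.1 looks like a slip, because the hypotheses in the same section keep it.

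These points stand, and they make the bias conditional. They do not remove the contradiction, which is in the protocol's own text on a primary comparison. Nor do they show how a condition tied to the 7th injection would be evaluated equally in Arm A when the protocol says its nearest visit may be absent or off schedule.

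**Conclusion.** The point holds in this form: the Comparison 2 population is defined inconsistently, and one of its definitions conditions on status about 4 weeks after time zero (28 ± 7 days, at most 8 weeks). That much is certain from the text.

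The inflation is a risk, not a demonstrated property of the plan. At a 4-week gap it runs from about 0.125 if a quarter of gap events leave Arm C only, through 0.16 for half, to 0.23–0.24 for all. It is absent if the arms are handled identically. No document figure fixes the share dropped, and the 8-week result of 0.41 is an extreme case.

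The power mismatch does not depend on that asymmetry. It rests on benefit starting only from the 7th injection, in line with Section 8.6, and on 75 events. Under those terms the 6th-dose rule in the synopsis and Section 8.6 has about 71–72% power instead of 80.6%.

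**What to change.** State one set in the same words in Section 8.2, H02/HA2, Section 8.4.1 and Section 8.4.2.2, and align the synopsis and Section 8.6 with it: all randomized Arm A and Arm C subjects who received 6 injections and are alive and SSE-free at time zero, analysed as randomized. Delete the clause on eligibility at Week 24 or the 7th injection, and put no condition on anything after time zero.

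Then choose one start:

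1. Keep the 6th dose as time zero and restate the power in Section 8.6 at about 71–72% for 75 events.
2. Use a common landmark of 6th dose plus 28 days in both arms, requiring subjects to be alive and SSE-free at that landmark. This keeps about 80% power.

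The cost is mainly wording in the protocol and SAP. Option 1 lowers the stated power. Under either option, Arm C subjects who never receive a 7th injection stay in the set, which somewhat dilutes any effect. An intention-to-treat comparison of Arm A with Arm C from randomization could be added as an optional sensitivity analysis.
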